7.9. Study Procedures

7.9.1. Informed Consent

Prior to initiation of any study related procedures, patients will be informed about the nature and purpose of the study, participation and termination conditions, and risks and benefits. Patients will be given the opportunity to ask questions of site personnel and to discuss with family or friends if they wish. After a patient has had ample opportunity to consider the information provided, they will be asked to sign the study's informed consent form to participate in the study.

7.9.2. Review of Eligibility, Medical History, Prior Treatment, and Medications

Eligibility criteria (inclusion and exclusion criteria), medical history (including OA history), and prior treatment and medications are reviewed during screening and again at Day 1.

OA medical history includes ACR diagnosis details, OA diagnosis date (if available), number of days with pain in both knees in the last month, and previous IA steroid or hyaluronic injections.

7.9.3. Physical Examination

The physical exam will assess the following body systems:

1. General Appearance
2. Skin
3. Lymphatics
4. HEENT (head, ears, eyes, nose, throat)
5. Cardiovascular
6. Respiratory
7. Abdominal
8. Musculoskeletal
9. Neurological

Any clinically significant findings, outside of the typical disease state, must be documented in the source and added to the medical history if found at Screening or recorded as an AE if new or worsened from pre-dosing on Day 1.

7.9.4. Index Knee X-ray

A diagnostic quality X-ray of the index knee is required (standing, fixed flexion PA view; weight-bearing; use of standardized knee positioning device is required) at Screening. The X-ray will be sent to the central imaging vendor for K-L grading, the presence of osteophytes (both required for eligibility), and joint space width. An image acquisition manual will be distributed to sites with simple instructions for radioanatomic positioning for reliable grading.

7.9.5. Index Knee Ultrasound

A diagnostic quality ultrasound of the index knee is required within -10 days prior to Day 1/Baseline. The ultrasound will be read locally for inflammation. Please refer to [Schedule of Study Assessments](#) for specific timing requirements.

7.9.5.1. Machine Capabilities

The machines used in the study should be able to distinguish the edge of proliferated synovium from the surrounding periarticular fat. For the patient with a higher BMI, a lower frequency transducer capability e.g., 7.5-10 MHz should be available, with a normal scanning frequency expected between 10MHz and 15 MHz being optimal. All scanning will be performed with a linear transducer.

7.9.5.2. Scanning Method

The knee will be scanned in a semi-flexed position, approximately 30 degrees from horizontal, with the knee supported if needed. The transducer will be held in a longitudinal, midline position superficial to the quadriceps tendon. The suprapatellar recess will be located below the tendon. The pouch will be examined to its most proximal extreme. Synovial proliferation will be confirmed in a transverse view but measured in a longitudinal view only.

The measurement will be an average of synovial thickening of the opposite anterior and posterior surfaces of the pouch.

To measure, gentle pressure will be applied by the transducer in order to displace any fluid. Once the anterior and posterior surfaces are gently touching, a total measurement of synovial thickness is made using the machine's built-in electronic callipers. This measurement is recorded in mm. This is then divided by two to give an average single membrane measurement. The use of ≥ 2 mm thickening synovium will define abnormal synovial thickening.

7.9.5.3. Image Capture

The best representative image should be captured, correctly labelled (left or right knee), and saved in both a longitudinal and transverse view. The same longitudinal image used to show the electronic callipers will be saved. The thickness of the synovium will be displayed on the screen in mm. For further external verification, a 5 second video sweep of the pouch should also be captured.

7.9.6. Index Knee MRI with Contrast

A diagnostic quality MRI with a gadolinium-based contrast agent of the index knee is required within 10 days prior to Day 1/Baseline, and then again at Week 6 and Week 24 (+/- 7 days).

Once eligibility is confirmed, a pre-treatment MRI will be obtained and submitted to the central imaging facility to confirm image quality. Documentation of a quality MRI is needed prior to Day 1/Baseline. If the initial pre-treatment MRI fails quality control (QC), another MRI will need to be completed prior to Day 1/Baseline but at least 3-4 days after the initial MRI to ensure that that contrast agent has washed out.

All subsequent images (Week 6 and 24) will need to be completed on the same machine with the same coil and software as the Pre-treatment image and will need to be submitted to the central imaging vendor to confirm image quality. If the image does not pass QC, another MRI will need

to be completed within the +/- 7 day visit window but at least 3-4 days after the initial MRI to ensure that that contrast agent has washed out.

An MRI image acquisition manual will be distributed to sites with detailed technical instructions and specifications for imaging sequences, imaging coil and Field of View (FOV) positions.

The MRI will be analyzed centrally for the primary endpoint as well as the secondary and exploratory endpoints based on imaging.

7.9.7. Index Knee Assessment

The index knee assessment will be performed by the designated assessor at the days indicated in the [Schedule of Study Assessments](#). The index knee will be assessed for tenderness, heat/redness, swelling, effusion, and Baker's cyst. If there is a clinically significant finding outside of the patient's typical disease state at the Screening or Day 1 Visit (pre-injection), add to the Medical History. At time points post-injection, if there are new clinically significant findings or findings that worsen for the patient's baseline condition, record as AEs.

7.9.8. 12-lead ECG

At Screening, a 12-lead ECG will be obtained in the supine position. Measures of heart rate, PR interval, RR interval, QT interval, QT interval corrected for heart rate (QTc) (corrected for Bazett's or Fridericia's) interval, and QRS duration will be obtained. ECGs will be locally read and a copy of each recording will be kept with the patient's source documentation. If any abnormality is determined to be clinically significant by the Investigator, the patient would be a screen failure.

7.9.9. Vital Signs

Vital signs are to be taken at the days indicated in the [Schedule of Study Assessments](#). The following measurements will be taken: sitting blood pressure, heart rate, respiration rate, and temperature.

7.9.10. Height, Weight, and BMI Determination

Height and weight are to be taken at the days indicated in the [Schedule of Study Assessments](#). Height will be measured in centimeters (cm) or inches. Weight will be measured in kilograms or pounds. BMI will be calculated using the formulas in [Table 2](#) (reference: www.cdc.gov):

Table 2: BMI Calculations

Measurement Units	Formula and Calculation
Kilograms and meters (or centimeters)	
Formula: weight (kg) / [height (m)]²
 
With the metric system, the formula for BMI is weight in kilograms divided by height in meters squared.
 
If, as common, height is measured in centimeters, divide height in centimeters by 100 to obtain height in meters.
 
Example: Weight = 68 kg, Height = 165 cm (1.65 m) Calculation: $68 \div (1.65)^2 = 24.98$

Pounds and inches	
Formula: weight (lb) / [height (in)]² x 703
 
Calculate BMI by dividing weight in pounds (lbs) by height in inches (in) squared and multiplying by a conversion factor of 703.
 
Example: Weight = 150 lbs, Height = 5'5" (65") Calculation: $[150 \div (65)^2] \times 703 = 24.96$

7.9.11. Synovial Fluid Aspiration

Synovial fluid samples for potential future biomarker evaluation will be obtained from all patients via aspiration on Day 1 prior to study medication administration. The injector/aspirator will attempt to aspirate synovial fluid from the knee using sterile technique. The volume of the synovial fluid obtained will be recorded in the eCRF. If no synovial fluid is obtained then 0 mLs should be recorded. Procedures for sample collection, handling, storage, and shipment will be described in the Central Laboratory Manual. The synovial fluid samples will be preserved for potential future analyses of biomarkers that may contribute to the pathogenesis of OA and/or be associated with responsiveness to FX006 treatment.

7.9.12. Central Clinical Laboratory Evaluations

Blood samples will be taken at the days indicated in the [Schedule of Study Assessments](#). The specific laboratory panels to be run can be found in [Table 3](#). Follow the Central Laboratory Manual for detailed sample collection, handling, storage, and shipping instructions.

Table 3: Clinical Laboratory Panel

Hematology	Clinical Chemistry
Hemoglobin	Sodium
Hematocrit	Potassium
Erythrocyte count (red blood cells [RBC])	Bicarbonate
Mean cell volume	Chloride
Leukocytes (white blood cells [WBC])	Calcium
Absolute counts of:	Total bilirubin
• Neutrophils	Alkaline phosphatase
• Lymphocytes	Alanine aminotransferase
• Monocytes	Aspartate aminotransferase
• Eosinophils	Blood urea nitrogen
• Basophils	Creatinine
• Platelets	Uric acid
	Glucose
Infectious diseases	Total protein
Hepatitis B Surface Antigen	Albumin
Hepatitis C Virus Antibody ¹	
HIV ²	
Other	
IL-1 β mRNA levels	
eGFR	
Pregnancy tests (females of child-bearing potential only)	
Serum: submitted to and performed by Central Laboratory	
Urine: test provided by central laboratory but performed and read at the site	

1. Patients positive for HCV Antibody will have reflex testing for circulating HCV RNA.

2. HIV screening will use a current 4th generation test for both antibody and viral antigen.

7.9.13. Patient Questionnaires

The following questionnaires will be completed by patient prior to all other assessments scheduled for the visit day at the days indicated in Table 1.

- WOMAC[®] LK 3.1
- KOOS - Quality of Life Subscale (Q1-Q4)
- Supplemental Pain and Stiffness Questions

7.9.14. Treatment Administration

At Day 1, and after completion of all required assessments, the following will occur:

- Study medication will be prepared by the pharmacist/coordinator. Refer to the Pharmacy Binder for FX006 dose preparation instructions.
- Synovial fluid will be aspirated from the index knee just prior to administration of study medication (refer to Section 7.9.11 for more details of the synovial fluid aspiration).

- The injector/aspirator will perform the IA injection of the study medication (refer to Section [7.5.8](#) for instructions).

7.9.15. Review of Adverse Events and Concomitant Medications

Subjects will be monitored for adverse events from signing of informed consent through the end of their participation in the study. Refer to Section [8.4.1](#) for further information about reporting of AEs.

Review of any Concomitant Medications will also be performed and documented in source documentation. Refer to Section [7.6](#) for further information regarding allowed and restricted concomitant medications and therapies.

8. ADVERSE EVENTS

Subjects will be monitored for adverse events from signing of informed consent through the end of their participation in the study.

Between the signing of the informed consent and initiation of study medication, only serious adverse events will be recorded on the eCRF. Following the start of study drug administration, all treatment-emergent adverse events, including serious adverse events, will be collected through the Final Visit. Results of clinical safety assessments are to be recorded in the patient's medical records and transcribed to the appropriate eCRF, including the AE eCRF for clinically significant findings.

8.1. Definitions

Adverse Event (AE): An AE is any untoward medical occurrence in a patient or clinical investigation subject administered a pharmaceutical product and that does not necessarily have a causal relationship with this treatment. An AE can therefore be:

- Any unfavorable and unintended sign (including an abnormal laboratory finding), symptom, or disease temporally associated with the use of a medicinal (investigational) product, whether or not related to the medicinal (investigational) product.
- Any clinically significant abnormality found on an ECG, laboratory test, or physical examination.
- Any worsening (i.e., any clinical significant adverse change in frequency and/or intensity) of a preexisting condition, which is temporally associated with the use of the medicinal (investigational) product

Serious Adverse Event (SAE): An SAE is any untoward medical occurrence that at any dose:

- Results in death,
- Is life-threatening,
 - “Life-threatening” refers to an event in which the patient was at substantial risk of death at the time of the event; it does not refer to an event which hypothetically might have caused death if it were more severe.
- Requires inpatient hospitalization or prolongation of existing hospitalization,
 - Note: Adverse events requiring hospitalizations that are less than 24 hours in duration do not meet this criterion. A planned hospitalization for an elective procedure or a pre-existing condition that has not worsened during participation in the study does not meet this criterion.
- Results in permanent or significant disability/incapacity; a substantial disruption of the patient's ability to carry out normal life functions.
- Is a congenital anomaly/birth defect.

- Is an important medical event: event that may not be immediately life-threatening or result in death or hospitalization but may jeopardize the patient or may require intervention to prevent one of the outcomes listed in the definition above.

Planned Hospitalization:

A hospitalization planned prior to first dose of study medication is considered a therapeutic intervention. If the planned hospitalization or procedure is executed as planned, it should be recorded in the patient's medical history. However, if complications arise during the planned hospitalization or procedure or the patient experiences an AE during the planned hospitalization or procedure, it must be reported as an AE.

8.2. Monitoring of Adverse Events

At each visit, all AEs and SAEs that occur from the time of treatment and throughout a patient's study participation that are observed or reported by the patient, will be recorded in the source documentation and appropriate section of the AE or SAE eCRF.

The Investigator is required to follow SAEs until resolution or withdrawal of consent. Resolution is defined as:

- A return to baseline for a pre-existing condition;
- Resolved with or without residual effects;
- The Investigator does not expect any further improvement or worsening of the event;
- Fatal outcome: If an autopsy is performed on a deceased patient, the autopsy report should be provided to the Sponsor as soon as it is available.

8.2.1. Monitoring of Laboratory Assessments and other Diagnostic Tests

The Investigator will review results of laboratory and other diagnostic tests for clinical significance and consideration as an AE.

8.3. Assessment of Adverse Events

8.3.1. Assessment of Severity

Each adverse event should be evaluated for severity or intensity. This is not the same as "serious," which is based on patient/event outcome or action criteria usually associated with events that pose a threat to a patient's life or functioning. The severity of AEs will be assessed according to the following definitions:

- **Mild:** the AE is noticeable to the patient and/or the Investigator, but does not interfere with routine activity.
- **Moderate:** the AE interferes with routine activity, but responds to symptomatic therapy or rest.
- **Severe:** the AE significantly limits the patient's ability to perform routine activities despite symptomatic therapy.

8.3.2. Assessment of Relationship to Study Medication

A medically-qualified Investigator must assess the relationship of any AE (including SAEs) to the use of the investigational product, as **related** or **not related**, based on clinical judgment and using all available information, and may include consideration of the following factors:

- Possible alternative causes of the AE, including the disease under treatment, pre-existing conditions, concomitant use of other drugs, and presence of environmental or genetic factors.
- The temporal association between drug exposure and onset of the AE.
- Whether the manifestations of the AE are consistent with known actions or toxicity of the investigational product.

The causal relationship between the study medication and the AE will be assessed using one of the following categories:

Not Related: An AE is not associated with study medication if:

- Temporal relationship is lacking (e.g., the event did not occur within a reasonable time frame following administration of the study medication); **or**
- Other causative factors more likely explain the event (e.g., a pre-existing condition, other concomitant treatments).

Related: An AE is attributed to the study medication if:

- There is a positive temporal relationship (e.g., the event occurred within a reasonable time frame following administration of study medication); **and**
- The AE is more likely explained by the investigational product than by another cause (i.e., the AE shows a pattern consistent with previous knowledge of the investigational product or the class of the investigational product).

8.4. Recording of Adverse Events

All AEs, regardless of seriousness, severity, or causal relationship to study medication, will be recorded on the AE page of the eCRF.

If discernible at the time of completing an AE eCRF, a specific disease or syndrome rather than individual associated signs and symptoms should be identified by the Investigator and recorded on the appropriate AE eCRF. However, if an observed or reported sign, symptom, or clinically significant laboratory anomaly is not considered by the Investigator to be a component of a specific disease or syndrome, then it should be recorded as a separate AE on the appropriate AE eCRF.

8.4.1. Reporting of Serious Adverse Events

When an SAE occurs, the Investigator or designee, must log into the electronic data capture (EDC) system and complete the SAE report form within 24 hours of becoming aware of the SAE. The EDC system will notify the Medical Monitor and other appropriate study personnel of the SAE.

If the EDC SAE form is not available, the Investigator should complete and sign the paper SAE form and email it to the Sponsor. When the EDC system is available again, the SAE should be input into the SAE form.

Follow up information relating to an SAE must be reported to the Sponsor within 24 hours of receipt by the Investigator by entering new or updated information into the EDC SAE form.

All SAEs that occur at your site should, in addition, be reported by the Investigators to the responsible IRB/EC without undue delay, if applicable according to IRB/EC requirements.

During the conduct of the study, the Sponsor will provide expedited safety reports (AEs classified as serious, unexpected and related to study medication) to the investigative sites. If this occurs, the investigative site must report the information to their IRB per local guidelines (may be submitted by the Sponsor or designee for sites that use a central IRB).

8.4.2. Safety Monitoring Roles

The site personnel will carefully monitor each patient throughout the study for possible AEs. All AEs will be reviewed and assessed by the Investigator.

The Sponsor must promptly review all information relevant to the safety of an investigational new product received from any source including AE data individually and in aggregate throughout the course of the study.

Investigators will receive prompt notification of any adverse experience associated with the use of the study medication that is both serious and unexpected, or any finding that suggests a significant risk for patients. The Investigator will promptly inform the IRB/EC of the notification and insert the notification in the Investigator's Regulatory Binder in accordance with local regulations.

The medical monitor and the Sponsor will review the study's safety data approximately on a quarterly basis, in order to identify potential safety issues/trends that may not be apparent through individual AE reporting. If systematic review identifies a concern, the Sponsor will take steps to address the issues including, but not limited to, modifying the protocol or Informed Consent, and/or notifying investigators, authorities and IRB/ECs.

8.4.3. Clinical Management of Index Knee Related Events

If the patient has an immediate reaction following administration of study medication or returns to the clinic with an acute exacerbation (e.g., tenderness, increased pain, swelling, effusion, decreased mobility of the index knee), the patient should be treated according to local clinical guidelines and physician experience.

If the index knee is aspirated at any time after administration of study medication for any reason, the volume of synovial fluid aspirated must be documented, synovial fluid should be (1) cultured, (2) evaluated for presence of crystals and (3) assessed for white cell count at a local laboratory, and the results should be documented.

Any event that is a change from the patient's baseline status (new or worsening case) should be reported as an AE and those meeting the definition of serious must be reported in accordance with Section 8.4.

8.4.4. Pregnancy

All pregnancies, female patients or female partners of male patients during the study, must be reported within 24 hours on the Pregnancy Report Form. The Investigator must continue to follow the pregnancy until the completion of the pregnancy, including the outcome and the condition of the newborn (if applicable). If not all information on the Pregnancy Report Form is available at the time of the initial report, follow-up reports should be provided to the Sponsor in a timely manner. Additional subsequent follow-up is not needed when a newborn baby is healthy.

9. STATISTICAL CONSIDERATIONS

9.1. Statistical and Analytical Plans

Key aspects of the proposed statistical analyses are summarized below. A comprehensive Statistical Analysis Plan will be written and approved prior to database lock for this study. If, after the study has been completed, changes are made to the statistical analysis plan referenced below, these deviations to the plan will be listed in the Clinical Study Report (CSR), along with an explanation as to why they occurred.

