- The Synovitis Imaging Population will include all patients from the Safety Population who have a pre-treatment synovial volume measurement of greater than 3000 mm³ of gadolinium enhancement as determined by quantitative image analysis, as well as quality pre-treatment and Week 6 MRIs. In addition, the patients included in this population will have no major protocol deviations and/or imaging variations (i.e. change in coil, machine, or software) deemed to potentially impact the imaging analysis.
- The Imaging Population will include all patients from the Safety Population, who have quality MRI data available for pre-treatment and at least one post- baseline timepoint and with no major protocol deviations and/or imaging variations (i.e. change in coil, machine or software) deemed to potentially impact the imaging analysis.
- The Efficacy Population will include all patients from the Safety Population, who have at least one post-Baseline/Day 1 WOMAC or KOOS assessment.

Demographic and baseline characteristics will be listed by study site and patient and will be summarized. Frequencies and proportions will be presented for the categorical variables and descriptive statistics will be presented for continuous variables.

Primary efficacy analysis will be the mean standardized change from baseline at 6 weeks in synovial volume will be determined and the 95% confidence interval (CI) will be calculated. Secondary efficacy analyses include an absolute change (mm³) from baseline at 6 weeks in synovial volume will also be calculated and the 95% CI will be presented. Standardized and absolute change from baseline will also be analyzed for synovial volume at 24 weeks.

Descriptive statistics and the 95% CIs will be calculated on pain, stiffness, function and quality of life. Other efficacy variables such as structural and contrast changes in bone, cartilage and other tissues based on the MRI results will be provided in the SAP and described in the Imaging Manual. A responder/non-responder analysis will be conducted to describe associations between physiological and functional/QOL measures and MRI results

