9.1.1. Interim Analysis

Once all enrolled patients in the Synovitis Imaging Population have completed the Week 6 visit the mean standardized change from baseline at 6 weeks in synovial volume (the primary endpoint) and other efficacy measures, will be analyzed. Safety analyses may be included and will be detailed in the SAP. Full results of this interim analysis will be presented to the Sponsor.

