9.1.2. Final Analyses

Once all enrolled patients have completed the Week 24 visit, all final analyses specified in the SAP will be completed following database lock and reported in the CSR. Post-hoc, exploratory analyses, may also be performed to further understand and elucidate study results; these analyses will be clearly identified as such in the CSR.

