9.2.1. Analysis Populations

Complete details of the statistical analysis will be specified in the SAP. Four analysis populations are planned for this study as follows:

- The Safety Population will include all patients who receive study drug. The Safety Population will be used to assess safety and tolerability.
- The Synovitis Imaging Population will include all patients from the Safety Population, who have a pre-treatment synovial volume measurement of greater than 3000 mm³ of gadolinium enhancement as determined by quantitative image analysis, as well as quality pre-treatment and Week 6 MRIs. In addition, the patients included in this population will have no major protocol deviations and/or imaging variations

(i.e. change in coil, machine or software) deemed to potentially impact the imaging analysis.

- The Imaging Population will include all patients from the Safety Population, who have quality MRI data available for pre-treatment and at least one post baseline timepoint and with no major protocol deviations and/or imaging variations (i.e., change in coil, machine or software) deemed to potentially impact the imaging analysis.
- The Efficacy Population will include all patients from the Safety Population, who have at least one post-Baseline WOMAC or KOOS assessment.

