9.4.3. Efficacy Analyses

Primary efficacy endpoint:

- Mean standardized change from baseline at 6 weeks in synovial volume

Secondary efficacy endpoints:

- Mean absolute change (mm³) from baseline at 6 weeks in synovial volume
- Mean standardized change from baseline at 24 weeks in synovial volume
- Mean absolute change (mm³) from baseline at 24 weeks in synovial volume

Analysis of additional secondary and exploratory endpoints will be defined in the SAP.

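### The SAP need only be approved before a lock that follows Week 24, although the Sponsor sees the complete Week 6 primary result earlier; SAP approval and the CSR listing rule should be tied to the Week 6 analysis

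*Protocol*

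**What the plan says.** Section 9.1 sets the deadline for the plan: "A comprehensive Statistical Analysis Plan will be written and approved prior to database lock for this study". It also sets the disclosure rule. CSR listing with an explanation is triggered as follows: "If, after the study has been completed, changes are made to the statistical analysis plan referenced below".

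Section 9.1.1 times the interim analysis: "Once all enrolled patients in the Synovitis Imaging Population have completed the Week 6 visit". At that point the primary endpoint and other efficacy measures are analysed, and "Full results of this interim analysis will be presented to the Sponsor".

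Section 9.1.2 places the only database lock that the protocol mentions: "Once all enrolled patients have completed the Week 24 visit, all final analyses specified in the SAP will be completed following database lock".

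Two elements of the primary analysis are left to interpretation. Section 9.4.3 names the primary endpoint as "Mean standardized change from baseline at 6 weeks in synovial volume" without saying what the change is standardized by. Section 9.2.1 removes patients from the Synovitis Imaging Population for major protocol deviations or imaging variations "deemed to potentially impact the imaging analysis", without saying who judges this or by when.

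**The concern.** What the protocol calls an interim analysis is, for the primary endpoint, the complete analysis. Membership of the Synovitis Imaging Population requires a usable Week 6 scan, so once those patients have had their Week 6 visit no further primary data will accrue. The Sponsor then holds the full primary result while the SAP may still lawfully be unapproved or open to revision.

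The trial is single-arm and open-label, so neither blinding nor a control group restrains choices made in the light of the result. A SAP approved beforehand is one of the main protections left. Under the stated rules, a definition or an exclusion changed after the Week 6 result but before lock would count as pre-specified, and Section 9.1 would not require the CSR to list it. A reader relying on that rule could not tell which choices preceded the result.

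Repeated testing is not the issue. The Week 6 endpoint is analysed on complete data, and no alpha adjustment is called for.

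**Working it through.** The protocol gives no figure to reproduce here. The check is first of the order of events, then of how much the open choices could move the result.

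**Order of events**

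| Event | Timing in the protocol |
|---|---|
| Primary endpoint analysed, full results to the Sponsor (9.1.1) | after the last Week 6 visit in the Synovitis Imaging Population |
| Database lock (9.1.2) | after the last Week 24 visit of all enrolled patients |
| SAP approval deadline (9.1) | any time before that lock |
| CSR listing duty begins (9.1) | study completion |

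Both the deadline and the listing duty fall after the primary result may be known. For one patient the two trigger visits are 24 − 6 = 18 weeks apart. With the ±7-day visit windows in Table 1 the range is (24 − 1) − (6 + 1) = 16 to (24 + 1) − (6 − 1) = 20 weeks. This is not the interval between delivery of the result and lock, for which the protocol gives no dates.

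**Judged exclusions**

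Inputs: 70 evaluable patients (Section 9.3). Assumptions: normally distributed changes, and k = 1, 2 or 3 patients excluded from 70 + k. All shifts are in SD units of the change.

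- 95% CI half-width at n = 70: t(0.975, 69)/√70 = 1.995/8.367 = 0.238.
- Exclusion unrelated to outcome: the mean shift is 0 on average, with SD √(1/70 − 1/(70 + k)).
- Worst case: exactly the k least improved patients are removed (40,000 simulated samples for each k).

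| k | SD of shift, unrelated to outcome | % of half-width | Worst-case shift | % of half-width |
|---|---|---|---|---|
| 1 | 0.014 | 6% | 0.034 | 14% |
| 2 | 0.020 | 8% | 0.063 | 26% |
| 3 | 0.024 | 10% | 0.089 | 37% |

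The worst case is a bound and not a forecast.

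**Meaning of standardized**

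Dividing every change by one common SD rescales the mean and its standard error together, so the one-sample t-statistic is unchanged (correlation 1.000). Percent change is a different quantity. In 4,000 simulations at n = 70 the correlation between the t-statistics for raw and percent change was 0.96 with a baseline CV of 0.3, and 0.90 with a CV of 0.5. These simulations assumed lognormal baseline volumes and a change SD proportional to the square root of baseline. The choice of scale therefore alters mainly how the effect size is presented.

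**The case against.** The strongest reply is that little is really open. The interim trigger names the Synovitis Imaging Population and the analysis uses the standardized change, so both must have a working form before any result exists; what remains is later revision. That is correct, and it narrows the exposure to revision or late formal approval.

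Several safeguards also stand:

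- Time point, threshold of more than 3000 mm³, 95% CI and two-sided 0.05 level are fixed in the protocol, and changing protocol text requires Sponsor approval and normally IRB/EC approval (Section 11.5).
- Section 7.9.6 requires follow-up scans on the same machine, coil and software, with central confirmation of quality.
- The Synopsis requires that the absolute change "from baseline at 6 weeks in synovial volume will also be calculated and the 95% CI will be presented", so a reader can set any rescaled result beside the raw one.
- Section 9.1.2 requires post-hoc analyses to be labelled.

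None of these settles how the change is standardized or how the exclusion judgement is applied before the result is seen. The labelling rule does not clearly catch a definition written into a SAP that was still open.

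It can also be said that a formula and detailed deviation rules belong in the SAP. They do, and their absence from the protocol is not the complaint. The approval deadline and the listing rule are protocol text, and those are what is badly fixed. Section 9.1.1 refers interim safety analyses to the SAP, which suggests that a SAP was expected by then, but it sets no date. The protocol mentions no separate Week 6 lock. Finally, the CSR rule does not forbid listing earlier changes; it simply does not require it.

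**Conclusion.** The point holds and should be fixed. On the protocol's own wording, the SAP may be approved or revised after the Sponsor has the complete primary result, and a revision made before study completion falls outside the CSR listing duty. The SAP was not available for this check and may in fact have been approved in time; the protocol does not require it.

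The likely numerical effect is small. A worst-case exclusion of three patients would move the mean by about a third of the CI half-width, and ordinary exclusions by about a tenth or less. Those sizes rest on assumed normal changes and an assumed one to three exclusions; the scaling results rest on an assumed baseline distribution and variance relation. The conclusion about timing and traceability rests on none of these assumptions.

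**What to change.** Make two wording changes in Section 9.1:

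1. Require that the SAP is approved, and that membership of the Synovitis Imaging Population is fixed and documented, before the Week 6 interim analysis is run.
2. Start the CSR listing rule at the running of the Week 6 interim analysis instead of at study completion, so that every later change to the SAP or the population is listed with its reason.

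Freezing the Week 6 data and central MRI reads at the same point would be a sensible addition.

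The cost is earlier SAP sign-off and earlier review of deviations and imaging variations for the Week 6 scans, much of which the interim analysis needs anyway. A data freeze would add earlier cleaning of those data. No extra patients, visits or data collection are involved.
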